Clinical Investigation Plan

CP345 The ASSISTER Trial

A r**A**ndomized cro**SS**-over trlal inve**ST**igating H**E**ylo, a novel app driven digital supporting ostomy p**R**oduct

October 2021 - December 2022

Approval date: 19 August 2021

NCT05200416

CHANGE LOG

VERSION NUMBER	ISSUED BY (INITIALS)	COMMENTS (MAJOR CHANGES SINCE LAST REVISION)
1.0		First approved version

This confidential document is the property of Coloplast A/S. No unpublished information contained herein may be disclosed without written approval of Coloplast A/S.

SYNOPSIS OF THE CLINICAL INVESTIGATION

CP345 The ASSISTER Trial – A randomized cross-over trial investigating Heylo, a novel app driven digital supporting ostomy product.

Test products and comparator:

- Adhesive layer with a build-in sensor system (single use)
- Transmitter (re-use), to be connected to the sensor layer.
- Heylo™ app (installed on subject's own smartphone). The app is communicating sensor status to the subject.
- · Charger to the transmitter incl. core

The comparator products in this study are Standard of Care which is defined as subject's own ostomy product.

Intended use:

Heylo $^{\text{TM}}$ is intended to be used together with an ostomy baseplate and bag, to detect and notify user of the occurrence of output leakage under an ostomy baseplate.

Objectives:

Primary objective: Is to investigate whether Heylo[™] can improve the emotional impact (measured by the Leakage scale questionnaire (OLI)), compared to Standard of Care.

Secondary objective: Is to evaluate whether Heylo[™] can improve participation in everyday and social activities compared to Standard of Care.

Design of the investigation:

The clinical investigation is an open-labelled, randomized cross over trial evaluating $\mathsf{Heylo}^\mathsf{TM}$ and $\mathsf{Standard}$ of Care .

Study visits will be conducted at the subject's home or through remote virtual calls.

Each of the subjects will have an inclusion visit (V0) and a baseline visit (V1) and two test visits - V2 and V3, including Termination visit carried out by the Principal Investigator, or delegate.

At V1, V2 and V3 the Principal investigator or delegate and the subject will complete questionnaires and every 2^{nd} week the subject will be asked to complete questionnaires. All questionnaires will be completed using a remote electronic data capturing method.

A follow-up call will be scheduled 7 days ± 2 days after visit 1 and visit 2 to ensure compliance with the provided investigational device and study procedures and insurance of subject's wellbeing. Additional calls/visits may be scheduled if needed, assesses by the PI or delegates, and will be registered as unscheduled visits.

Expected duration of the clinical investigation:

The expected duration of the investigational period is 16 weeks (±6 days). Each Test period is 8 weeks (±3 days).

Primary endpoint, Secondary endpoint, and Exploratory endpoints:

Primary endpoint: Emotional impact score (scale from 0 - 100) measured by the validated OLI scale evaluated at the end of each test period. See Appendix 1

Secondary endpoint: Participation in society domain score (scale from 0 - 100) measured by WHODAS evaluated at the end of each test period. *See Appendix* 3

Exploratory endpoints:

• Impact on Usual and social activities score (scale from 0-100) measured by the validated OLI scale evaluated at the end of each test period. See Appendix 1

- Impact on Coping and in Control score (scale from 0-100) measured by the validated OLI scale evaluated at the end of each test period.
 See Appendix 1
- Feeling of security evaluated at the end of each test period. Question: "How was the feeling of security while wearing the product?" Answers: Very poor/Poor/Acceptable/Good/Very good.
- Understanding and communicating domain score (scale from 0-100) measured by WHODAS evaluated at the end of each test period.
 See Appendix 3
- Getting around domain score (scale from 0-100) measured by WHODAS evaluated at the end of each test period.

See Appendix 3

- Self-care domain score (scale from 0-100) measured by WHODAS evaluated at the end of each test period. See Appendix 3
- Getting along with people domain score (scale from 0-100) measured by WHODAS evaluated at the end of each test period
 See Appendix 3
- Life activities (household and work) domain score (scale from 0-100) measured by WHODAS evaluated at the end of each test period
 See Appendix 3

Population/subjects

The clinical investigation will be conducted in 144 subjects with ileostomy or colostomy with liquid/mushy output.

To be included in the investigation, the subjects must comply with the criteria presented below.

Inclusion criteria:

- 1. Has given written consent to participate by signing the Informed Consent Signature Form.
- 2. Is at least 18 years of age and has full legal capacity.
- 3. Has an ileostomy or colostomy with consistent liquid/mushy fecal output (5-7 Bristol scale*) *See appendix 2.
- Is able to use one of the five test products (i.e. Ø40, Ø50, Ø60, Ø70, Ø80 mm).
- 5. Has experienced leakage** under the baseplate at least three times within the last fourteen days. **Leakage defined as output seeping under the baseplate" See Appendix 5, Figure 2-5.
- Has worry about leakage to "some degree, high degree, or very high degree" (on a five-point Likert scale: Very low degree/Not at all, Low degree, some degree, High degree, very high degree)
- 7. Is willing to refrain from use of ostomy paste.
- Has a smartphone compatible with the Heylo™ application
- Is able to follow study procedures for 4 months (assessed by investigator or delegate)

Exclusion criteria:

- 1. Is participating in other clinical investigations or has previously participated in this investigation
- 2. Is pregnant or breastfeeding
- 3. Has known hypersensitivity towards any of the products used in the investigation
- 4. Is using/ has a pacemaker

ABBREVIATION	WRITTEN OUT	EXPLANATION
ADE	Adverse Device Effect	See section 18.2
AE	Adverse Event	See section 18.1
ASADE	Anticipated Serious Adverse Device Effect	See section 18.4.2
CIP	Clinical Investigation Plan	
CRF	Case Report Form (paper or electronic)	Questionnaire to be used for data collection
СМ	Clinical Manager	
DQF	Data Query Forms	A DQF is a query specifically used in clinical research. The DQF is the primary data query tool from the sponsor to clarify discrepancies and ask the investigator for clarification. The DQF is part of the data validation process in a clinical investigation.
DD	Device deficiency	See section 18.3
EC	Ethics Committee	
IFU	Instruction For Use	
ш	Intention to Treat	
PI	Principal Investigator	Qualified person responsible for conducting the clinical investigation at an investigation site. If the clinical investigation is conducted by a team of individuals at an investigation site, the PI is the responsible leader of the team. Whether this is the responsibility of an individual or an institution can depend on national regulations.
РР	Per Protocol	
SADE	Serious Adverse Device Effect	See section 18.4.1
SAE	Serious Adverse Event	See section 18.4
USADE	Unanticipated Serious Adverse Device Effect	See section 18.4.3

> TABLE OF CONTENTS

1.	List of personnel involved in the Investigation				
1.1	. Sponsor representatives				
1.2	. Investigator	8			

1.2. Investigator

2. Rational/justification for conducting the clinical investigation

People with intestinal stomas (especially an ileostomy) can have, despite development of better ostomy products, problems with leakage which influence their quality of life negatively [1,2].

To overcome this, Coloplast has developed a new supporting ostomy product called Heylo™, which has an adhesive sensor layer that should be placed underneath the baseplate. The sensor layer consists of an electronic sensor system, that continuously detects moisture and output leakage underneath the baseplate. A transmitter connected to the sensor layer continuously evaluate the incoming information and sends a status to a smartphone software application, which based on a predefined flow decides which information to deliver to the user about the baseplate status.

A clinical study CP321 has been planned and initiated including 25 subjects in Denmark, to confirm technical readiness with Android and iOS software and will be concluded upon before initiation of present study.

The overall aim of this clinical investigation is to evaluate the benefits of the new supporting product, Heylo™ compared to Standard of Care.

3. Objectives of the clinical investigation

3.1. Objectives

Primary objective

Is to investigate whether Heylo™ can improve the emotional impact (measured by the Leakage scale questionnaire (OLI)), compared to Standard of Care.

Secondary objective

Is to evaluate whether Heylo™ can improve participation in everyday and social activities compared to Standard of Care.

4. Investigational device and comparator

The investigational device is a novel app driven digital supporting ostomy product called Heylo^M. Heylo^M is CE-marked.

The investigational device is used in combination with the ostomy baseplates usually used by the subject. Subjects will be supplied with a sufficient number of Heylo™ sensor layers to support their normal change routine.

The comparator in this study will be Standard of Care which is defined as subject's own ostomy product.

4.1. Description of Investigational device - Heylo™

Heylo™ consists of the following:

- Adhesive sensor layer with a build-in sensor system (single use)
- Transmitter (re-use), to be connected to the sensor layer.
- Heylo™ app (installed on subject's own smartphone). The app is communicating sensor status to the subject.
- Charger to the transmitter incl. core

[figure not shown]

Figure 1: Investigational device - Heylo™

Figure 2: Sensor layer

The colours on the sensor layer (Figure 2) are only illustrative and illustrate the different sensor elements.

- Turquoise: Outer leakage sensor. Detecting leak close to rim of baseplate
- Orange: Wear sensor. Detecting moisture absorbed by the adhesive material
- Purple: 3 inner leakage sensors. Detecting leak closest to stoma

The following sensor layer sizes will be available in the trial: Ø40, Ø50, Ø60, Ø70 and Ø80, referring to the inside diameter of the sensor layer.

The study nurse and subject will together find the right size of sensor layer that best fit the subject.

Figure 3: Sensor layer appliance

[figure not shown]

Figure 4: App data flow high level

If subjects have technical issues (e.g. technical failure screens delivered to users, and system does not seem to get back running again), they have the possibility to call a technical support service.

4.1.1. Manufacturing

Coloplast A/S, [name], is the manufacturer of the CE marked Investigational device.

4.2. Identification and traceability of the investigational device

The CE marked physical Test Product will be identified as Heylo™.

- Adhesive patch sensor layer ID
 - o ø40: 1921008000
 - o ø50: 1921108000
 - o ø60: 1921208000
 - o ø70: 1921308000
 - o ø80: 1921408000
- Transmitter ID 23323073
- Heylo™ app software version
 - o iOS 1.9.2.
 - o Android 1.9.2.
- Charger to the transmitter ID 23323072
- Charger cable ID: 23325128

4.3. Intended use of the investigational device in the clinical investigation

Intended purpose of device:

Heylo $^{\text{TM}}$ is intended to be used together with an ostomy baseplate and bag, to detect and notify user of the occurrence of output leakage under an ostomy baseplate.

Intended medical indications:

The product is indicated for subjects with an ostomy, mainly Ileostomy and colostomy with liquid output. The product is to be used on intact skin.

Intended mode of action:

The sensor layer is applied under an ostomy baseplate which is attached to the intact peristomal skin around the stoma. The sensor layer detects occurrence of output leakage under the ostomy baseplate and the subject is notified of the leakage via a smartphone software application.

Application:

In the Instruction for Use (IFU), application, few warnings, cautions and pre-caution of how to use Heylo^m are given. See IFU [5+6].

4.4. Intended population for the investigational device

Subjects with an ileostomy or colostomy with liquid/mushy fecal output (5 – 7 on the Bristol scale See Appendix 2) and with a certain degree of leakage and worry about leakage, are the intended population for this device.

4.5. Handling of the investigational device

The handling of Heylo™ is described in detail in the Instruction for Use (IFU), which is included in all boxes with the investigational device. Storage conditions are also stated in the IFU.

The PI (Principal Investigator) and PI delegate will receive training by sponsor and/or the PI in handling and correct use of the Investigational device. The PI or delegate will train the subjects in the correct use of the investigational device according to the IFU.

4.6. Total number of investigational devices intended for the clinical investigation

Each subject will be supplied with Heylo™ app and trial supplies as described below:

- 1 charger
- 1 charging cable
- 1 charging adapter
- Two transmitters
- Sensor layers to support a daily change pattern + sufficient extra sensor layers

4.7. Description of the comparator products

The comparator products in this study are standard of care which is defined as subject's own ostomy product.

5. Design of the clinical investigation

5.1. General

The clinical investigation is an open-labelled, randomized cross over trial evaluating Heylo™ and Standard of Care.

Subjects will use Heylo™ together with their own product (Baseplate and bag) during the test period with Heylo™ and in the Standard of Care period subjects will only use their own product (Baseplate and bag).

The expected duration of the total test period is 16 weeks (± 6 days). Each Test period is 8 weeks (±3 days).

In both test periods subjects will change ostomy products as usual, according to their normal change routine. Subjects may decide to change ostomy product earlier or later, based on a leakage notification.

Figure 5: Design of the clinical investigation

In total, 144 subjects will be included and randomized. Each of the subjects will have an inclusion visit (V0) and a baseline visit (V1) and two test visits - V2 and V3, including Termination visit carried out by the Principal Investigator, or delegate.

A follow-up call will be scheduled 7 days ±2 days after visit 1 and visit 2 to ensure compliance with the provided product and study procedures and Insurance of subject's wellbeing. Additional calls/visits may be performed if needed, assesses by the PI or delegates, and will be registered as unscheduled visits.

Before scheduling V0 the subject will be invited to an information meeting, where the PI or Study nurse will give a detailed information about the requirements and the content and what it involves participating in the investigation. The information meeting will be conducted as a phone call. See Section 6.2 for procedure for recruitment and enrolment.

Inclusion visit (V0) and baseline visit (V1) can be performed same day. If subject wishes to reconsider his/her participation at V0 after another oral review of the contents of the trial, the subject has the rights to wait minimum 24 hours before deciding on participation. If subject hereafter decides to participate in the clinical investigation, another date for V0 and V1 will be scheduled.

Study visits will be conducted at the subject's home or through remote virtual calls.

At V1, V2 and V3 the Principal investigator or delegate and the subject will complete questionnaires and every 2^{nd} week the subject will be asked to complete questionnaires. All questionnaires will be completed using an electronic data capturing method.

V3 will also be the termination visit unless a situation occurs where a subject terminates earlier than expected. If this is the case the subject will as the last visit have the termination visit performed.

5.2. Primary endpoint

Primary endpoint:

Emotional impact score (scale from 0 - 100) measured by the validated OLI scale evaluated at the end
of each test period.
 See Appendix 1

5.3. Secondary and Exploratory endpoints

Secondary endpoint:

Participation in society domain score (scale from 0 - 100) measured by WHODAS evaluated at the end
of each test period.
 See Appendix 3

Exploratory endpoints:

- Impact on Usual and social activities score (scale from 0-100) measured by the validated OLI scale evaluated at the end of each test period.
 See Appendix 1
- Impact on Coping and in Control score (scale from 0-100) measured by the validated OLI scale evaluated at the end of each test period.
 See Appendix 1
- Feeling of security evaluated at the end of each test period. Question: "How was the feeling of security while wearing the product?" Answers: Very poor/Poor/Acceptable/Good/Very good.
- Understanding and communicating domain score (scale from 0-100) measured by WHODAS evaluated at the end of each test period.
 See Appendix 3
- Getting around domain score (scale from 0-100) measured by WHODAS evaluated at the end of each test period.

See Appendix 3

- Self-care domain score (scale from 0-100) measured by WHODAS evaluated at the end of each test period. See Appendix 3
- Getting along with people domain score (scale from 0-100) measured by WHODAS evaluated at the end of each test period.
 See Appendix 3
- Life activities (household and work) domain score (scale from 0-100) measured by WHODAS evaluated at the end of each test period.
 See Appendix 3

Assessments:

- Leakage outside baseplate, evaluated end of each test period. Question: "Think back on the last 2
 weeks; how many times have you experienced stoma effluent leakage outside the baseplate (e.g. onto
 clothes or bedsheets)?" (number).
- Change in current stoma product, evaluated end of test period. Question: "Has there been any change
 in current stoma product during the test period?" (Yes/No) If yes, please add: Type (1pc/2pc), Kind (Flat,
 Convex, Concave), Brand (Coloplast, Hollister, Dansac, Salts, other)
- Change in Heylo size, evaluated end of test period. Question: "Change of Heylo size needed?" (Yes/no), if yes, please provide the new size: 40 mm, 50 mm, 60 mm, 70 mm, 80 mm
- Adverse events/device deficiencies

For Endpoint and assessment flowchart please see Appendix 4

5.4. Rationale for selection and measurement of endpoints

The primary and secondary endpoints have been chosen as they reflect expected benefits with use of Heylo. The two endpoints consist of the emotional impact domain and participation in everyday and social activities domain, and they are based on validated measurement tools. Evaluation of these quality of life domains as well as other questions related to coping and control, impact on usual and social activities, feeling of security, getting along with people, and life activities may together establish possible benefits of using Heylo compared to using Standard of Care alone.

5.5. Baseline information and potential compromising factors

Baseline/demographics

- Gender (male/female)
- Age (at time of enrolment (years)
- Height (cm)
- Weight (kg)
- Year of stoma creation (YYYY)
- Ostomy surgery within 3 months (yes/no)
- Reason for creation of the stoma (Crohn's disease/ulcerative colitis/ cancer/ Other)
- Stoma Type (ileostomy/colostomy)
- Temporary/permanent stoma
- Shape of the stoma (round/oval/irregular)
- Size of the stoma (widest diameter and height of stoma from skin)
- Information about the current stoma product: Type (1P/2P), Kind (Flat, convex, concave), Brand (Coloplast, ConvaTec, Hollister, Dansac, Salts, other)
- Working status (working, restricted duties, sick leave, unemployed/retired, student)

5.6. Equipment/methods and timing for assessing the variables

Please see Appendix 4 and section 7.1 and 7.2 for information regarding timing of endpoint data capture and section 11. for information on data collection.

5.7. Randomization procedure

All subjects that meet the inclusion and exclusion criteria will be randomized into one of two treatment sequences at V1, with a cross-over after 8 weeks (Visit 2). Subjects with stoma surgery less than 3 months, will be stratified according to time since surgery.

Treatment sequences:

Sequence A: Heylo™ + Standard of Care cross-over to Standard of Care

Sequence B: Standard of Care cross-over to Heylo™ + Standard of Care

When testing the Heylo™ it must be done together with subject's usual ostomy product and in the Standard of Care period subjects will only use their own product.

5.8. Blinding

No blinding will be used in this investigation, except for the statistician who will be blinded until Data Base Lock.

5.9. Total expected duration of the clinical investigation

The dates below are approximate, and no subjects will be enrolled before all required approvals have been obtained. If changes are required, applicable EC will be notified.

- First subject enrolled (10/2021).
- Last subject enrolled (06/2022).
- Last subject completed (10/2022).
- Final report (03/2023).

6. Clinical Investigation population

This clinical investigation will be conducted in Germany with up to 16 Coloplast Homecare nurses acting as study nurses. In this clinical investigation there will not be an regular Site. The PI who is responsible for conducting the

investigation will delegate study specific procedures to the study nurses, who will perform all study visits at the subjects home.

The clinical investigation will be conducted in 144 subjects with ileostomy or colostomy with liquid/mushy output (5-7 on the Bristol Scale).

The Principal Investigator will be overall responsible for the recruitment for the study and the Clinical manager in Germany will be responsible for the daily contact with the study nurses and the monitoring of the clinical investigation.

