- Schedule follow up call 7 days ±2 days after V1 to ensure compliance with the provided investigational device and study procedures and Insurance of subject's wellbeing.
- Schedule visit 2 in 8 weeks ±3 days

Visit 2 (V2), Week 8:

- Insurance of subject's wellbeing and follow-up on subject's compliance with study specific procedures (e.g. completing questionnaires and use of Investigational device + Standard of Care OR Standard of Care only)
- Subject completing todays questionnaires:
 - Emotional Impact (OLI)

- Coping and in control (OLI)
- Usual and Social activities (OLI)
- WHODAS 2.0:
 - Understanding and communicating
 - Getting around
 - Self-care
 - Getting along with people
 - Life activities
 - Participation in society
- Feeling of security, see section 5.3 and Appendix 4
- Assessment of:
 - o Leakage outside baseplate, see section 5.3 and Appendix 4
 - o Change in current stoma product, see section 5.3 and Appendix 4
 - o Change in Heylo size, if relevant, see section 5.3 and Appendix 4
 - o Review of AEs, ADEs, SAEs, SADEs, Device deficiencies and protocol deviations
- Instruct subject in installation of Heylo™ app (on subjects' own smartphone), if relevant
- According to the randomization, instruct subject in use of Heylo™ + Standard of Care or only Standard
 of Care for the next 8 weeks.
- Provide Investigation device Heylo™ after measurement of Heylo size, if relevant according to randomization.
- Instruct and remind the subject to follow the study specific procedures between visits, and inform subject to complete following questionnaires:
 - o Emotional Impact (OLI) every 2nd week
 - Coping and in control (OLI) every 2nd week
 - Usual and Social activities (OLI) every 2nd week
 - o Leakage outside baseplate 2nd week
 - WHODAS- every 4th week:
 - Understanding and communicating
 - Getting around
 - Self-care
 - Getting along with people
 - Life activities
 - Participation in society
- Collect unused Heylo™ devices from subjects who have tested these in the first 8 weeks.
- Collect used Heylo[™] devices (only charger and transmitter), from subjects who have tested these in the first 8 weeks
- Schedule follow up call 7 days ±2 days after V2 to ensure compliance with the provided investigational device and study procedures and Insurance of subject's wellbeing.
- Schedule visit 3 in 8 weeks ±3 days

Visit 3 – Termination Visit (V3), Week 16:

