11.1. Data collection and data management

11.1.1. Data Collection in the clinical investigation

Data management and the final statistical analyses of all measurements described in this protocol are carried out by the Medical Affairs, Coloplast A/S.

Data will be collected through an electronic data capturing (EDC) system on electronic Case Report Form (eCRF), internet-based case report form. This system will be used to record all subject information collected in the investigation for secure data tracking and centralised data monitoring ("remote monitoring") done by monitors, as defined in the monitoring plan.

The EDC system used is ______. The system is designed to be compliant with the FDA requirements of 21 CFR part 11. It is a validated data management system allowing only qualified and trained personnel to enter the system. The system has full audit trail and electronic signature.

The Principal Investigator or delegate will enter data in a part of the system referred to as the eCRF. The subjects will receive a link to the system to enter their registrations in a part of the system referred to as the subject questionnaire.

The sponsor will be responsible for training the investigator or delegate, in completion of the eCRF.

Principal Investigator, or delegate will perform primary data collection directly into the eCRF or drawn from source-document (medical records) reviews. The eCRF will be completed on a continuous basis starting from the point of enrolling the subject to final follow up.

The eCRF will be completed by the investigator, or delegate, who have signed the Site Personnel Signature and Delegation List and Clinical Investigation Training Log. It will be the responsibility of the Principal Investigator to ensure that all measurements and observations are correctly noted in the eCRF.

All assessments and observations throughout the investigation for each subject must be carefully recorded in an eCRF during the visit or immediately after. The eCRF makes it possible to enter data right away when they are obtained. This is the preferred way of collecting data. In case this is not possible the data should be entered no later than 7 days after the visit / procedure.

Adverse events should be registered following the timelines described in the Adverse Event section.

In the unforeseen situation, where clinical investigation personnel cannot establish connection to the EDC system a paper CRF (pCRF) has been printed and supplied by sponsor.

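### The week-8 questionnaires that carry the primary and secondary comparisons are tasks within visits run by the sponsor's own nurses in an open-label trial, and no rule puts the answers ahead of the nurse contact

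*Combined protocol and SAP*

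**What the plan says.** - **Who runs the visits.** Section 6 names "Coloplast Homecare nurses acting as study nurses". The principal investigator of the "investigation will delegate study specific procedures to the study nurses, who will perform all study visits at the subjects home". Section 5.1 and the synopsis also allow visits "or through remote virtual calls", so the contact may be in person or by call.
- **Blinding.** Section 5.8: "No blinding will be used in this investigation, except for the statistician who will be blinded until Data Base Lock".
- **When the week-8 forms are answered.** Section 5.1 says "At V1, V2 and V3 the Principal investigator or delegate and the subject will complete questionnaires". In section 7.1, the V2 (week 8) and V3 (week 16) lists each start with wellbeing and compliance, including use of the assigned product. The next item is "Subject completing todays questionnaires", which covers the OLI domains, WHODAS and feeling of security. Leakage outside the baseplate follows.
- **How they are answered.** Section 11.1.1: "The subjects will receive a link to the system to enter their registrations in a part of the system referred to as the subject questionnaire". Table 4 gives the OLI, WHODAS, security and leakage items to the subject. The synopsis describes electronic capture as remote.
- **Other weeks.** Between visits the subject completes the OLI and leakage items every second week and WHODAS every fourth week (section 7.1).
- **What is tested.** Section 10.1.2 makes the week-8 product difference the primary comparison. Section 10.1.3 uses a similar model for WHODAS participation at weeks 4 and 8. Under section 10.4 the trial succeeds if either endpoint is significant.
- **Safeguards.** Section 15.4 states that the nurses have no financial interest in the investigation. No section says that the week-8 answers come before the nurse contact or are given without nurse input.

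**The concern.** The primary endpoint is a subject's rating of feelings such as panic, worry and embarrassment (Appendix 1). The subject knows which product was used and, at week 8, answers during a contact with a nurse employed in the manufacturer's homecare service. A subject who has just used the manufacturer's new device may answer a little more favourably in that setting than one who has used only the usual appliance. Such a shift would favour Heylo at the time point on which both confirmatory comparisons rest.

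Weeks 2, 4 and 6 of the OLI are answered away from any visit. Only the deciding week is tied to the nurse contact, although the trial already has the means to collect it in the same way as the others.

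**Working it through.** **1. Inputs.** From section 10.2: paired two-sided t-test, test level 0.025, residual SD 14.4, 108 subjects answering at the end of both periods, planned difference 6, dropout 25%, stated power 81%, 144 included.

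**2. The plan's own figures.**
- SD of a within-subject difference = √2 × 14.4 = 20.36.
- SE of the mean difference = 20.36 / √108 = 1.96.
- Power for 6 points, normal approximation: Φ(6/1.96 − 2.241) = 79.4%. Exact paired t with 107 df: 78.4%. The plan states 81%, so the match is approximate. The small gap does not affect this point.
- Inclusion: 108 / (1 − 0.25) = 144, as stated.

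**3. Which nurse effects matter.** Write the week-8 score as a true value plus a setting effect: c under Standard of Care and c + b under Heylo. The week-8 product contrast is then the true difference + (c + b) − c = true difference + b. The common part c drops out. The model in section 10.1.2 has a product-by-time interaction, so week 8 has its own product contrast and a level shift confined to week 8 under both products goes into the time effect. Only b, the product-dependent part, biases the comparison.

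**4. What a given b would do.** The documents give no value for b. The values below are assumptions.
- Critical t (0.9875, 107 df) = 2.273, so the smallest significant difference is 2.273 × 1.96 = 4.45 points.
- With no true effect, P(significant in favour of Heylo) = P(T > 2.273), where T is noncentral t with 107 df and noncentrality b/1.96.

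| Assumed b (points) | Share of the planned 6 | b/SE | P(significant for Heylo) |
|---|---|---|---|
| 0 | 0% | 0 | 1.25% |
| 0.5 | 8% | 0.26 | 2.3% |
| 1 | 17% | 0.51 | 4.1% |
| 2 | 33% | 1.02 | 10.9% |

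These are one-direction figures. The nominal two-sided 2.5% gives 1.25% in each direction.

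**5. Is earlier completion feasible?** Subjects need a smartphone partly to answer the study questions (section 6.1.1) and are instructed in the questionnaire link at V1 and V2 (Table 4). They already complete the same OLI scale between visits. That the link can be open just before V2 and V3 is inferred from this use. No section says so, and none prevents it. The change alters neither the sample size, the test level nor the planned power.

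**The case against.** The strongest reply is that most of the protection is already there. The forms are electronic and self-completed, Table 4 assigns them to the subject, and visits may be by call. A reader might infer from section 5.1 that nurse and subject fill in the forms together, or that the nurse asks the questions and sees the answers at the visit. The documents do not support that: Table 4 gives the investigator separate items, such as change of stoma product and change of Heylo size. This part of the reply stands. What is missing is an ordering rule and a rule against nurse input.

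A reader might also infer that, because the model uses weeks 2 to 8 together and only week 8 is answered at a visit, the mixed setting by itself biases the week-8 result. With the product-by-time term it does not, as step 3 shows.

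The order of bullets in section 7.1 is not a prescribed sequence, and the compliance item applies under Standard of Care as well as under Heylo. That is fair. The plan permits the discussion to come first but does not require it.

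Two practical objections have some weight. Answering at the visit helps to secure the 108 pairs of end-of-period answers, so earlier completion needs a fallback. Hiding the answers from nurses altogether may need access changes, because section 9.1.3 gives delegated personnel access to all eCRFs and section 11.1.2 controls access by role.

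**Conclusion.** The point holds as a cheap improvement to conduct. It is not an error in the analysis. The plan leaves the week-8 subjective answers inside a contact with the sponsor's nurse, with no rule to limit a product-dependent wish to please at the moment of answering.

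The size is unknown. The rise from 1.25% to about 2.3%, 4.1% or 10.9% rests on assumed shifts of 0.5, 1 or 2 points, no true effect, 108 complete pairs and the section 10.2 variance. It applies to the primary endpoint only, since the plan gives no variance for WHODAS. A reader might take 10.9% as the harm done by the visit setting, or as what the change would save. Neither follows: subjects' knowledge of their product and their relationship with the nurse remain after the change, and no figure in the documents separates these sources.

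**What to change.** In sections 5.1 and 7.1 and in Table 4, state that:

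- the subject submits the week-8 OLI, WHODAS, security and leakage questionnaires through the personal link before the V2 or V3 visit or call begins, and within the ±3-day window;
- the nurse checks only that they were submitted;
- a subject who has not submitted completes them first at the visit or call, before any discussion and without nurse input;
- the setting (before the contact, or at it) is recorded for each form.

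The recorded setting also allows a descriptive look at whether the answers differ by setting.

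**Cost.** Protocol wording, one extra reminder through the existing system and one recorded item. No extra visit or staff. There is a small risk of late forms, which the fallback covers. A technical block on nurses viewing the answers is not required by this wording; if the sponsor wants one, role-based access would need review.
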